#### 5. Safety Analysis

Hypothesis 1f: The incidence of adverse events (AEs) will not differ between participants randomized to prazosin and those randomized to placebo. Fisher's exact test will be used to compare rates of dropout due to AEs between treatment groups.

Safety will be assessed by summarizing and analyzing AEs during the intervention period. AEs will be coded according to established Medical Dictionary for Regulatory Activities (MedDRA) terms and summarized by MedDRA System Organ Class (SOC) and Preferred Term (PT).

Treatment-emergent adverse events (TEAEs) will be defined as events that first occurred or worsened on or after randomization.

An overview of AEs, including the number and percentage of participants who died, suffered Serious Adverse Events (SAEs), discontinued due to AEs, and who suffered TEAEs, will be provided. A comparison between intervention arms will be performed.

The number and percentage of the following types of AEs will be reported:

- TEAEs
- All TEAEs
- TEAEs that led to study participant termination
- TEAEs related to study drug
- TEAEs by maximum severity
- SAEs
- All SAEs
- SAEs related to study drug
- AEs
- A listing of AEs will be reported

Summaries of AEs by within system organ class will be provided for the following:

- Preexisting conditions
- TEAEs
- SAEs
- Participant terminations due to AEs will also be listed

Blood Pressure (BP) and Heart Rate (HR)

Changes from baseline in supine (or sitting) and orthostatic (standing or sitting if unable to stand) systolic and diastolic BP and HR will be summarized using descriptive statistics. Similar analyses to that described for the primary analysis will be performed on supine and orthostatic systolic and diastolic BP and HR. An MMRM analysis will compare prazosin vs placebo at 12 weeks.

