#### 2. Power and Sample Size Determination

Power calculations for PEACE-AD were based on two-sample t-tests. Sample sizes were initially estimated targeting a power=80%, assuming a 2-sided alpha=5%, a standardized effect size of .44 SDs, and a dropout rate of 10%. This is a reasonable estimate of attrition given the study population and the relatively short follow-up period. Based on these considerations, 186 total participants are required: 124 in the prazosin group, and 62 in the control group.

Following COVID-19 in March 2020, it became clear that it would not be possible to successfully recruit this sample size to this protocol. In turn, a decision was made to change the focus to being a pilot trial of between 25-80 participants, a target number that was considered feasible in the aftermath of the pandemic. The range of sample sizes were then considered as a function of the standardized effect size delta; for delta = .71 the required sample size is 80 (53 in the prazosin group, and 27 in the control group), for delta = .79 the required sample size is 65 (43 in the prazosin group, and 22 in the control group), for delta = .91 the required sample size is 50 (33 in the prazosin group, and 17 in the control group), for delta = 1.0 the required sample size is 40 (27 in the prazosin group, and 13 in the control group), for delta = 1.2 the required sample size is 30 (20 in the prazosin group, and 10 in the control group).

The statistical analyses at study conclusion will be based on longitudinal regression data analysis that is expected to increase statistical power over the initial estimates with two-sample t-tests.

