#### 3.1 Safety Analysis Population

The safety analysis population is defined as those subjects that are randomized and took at least one dose of study drug. Categorical safety data will be analyzed, compared between treatment arms, using the exact contingency table method, Fisher's Exact Test.

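### Hypothesis 1f predicts no difference in adverse event incidence, but the test attached to it concerns dropout, and no adverse event comparison has an effect estimate or interval, so a non-significant result cannot support it

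*SAP*

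**What the plan says.** Section 5 of the SAP opens with Hypothesis 1f: "The incidence of adverse events (AEs) will not differ between participants randomized to prazosin and those randomized to placebo". The next sentence gives the analysis: Fisher's "exact test will be used to compare rates of dropout due to AEs between treatment groups".

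Further down, section 5 promises an overview giving "the number and percentage of participants who died, suffered Serious Adverse Events (SAEs), discontinued due to AEs, and who suffered TEAEs", and adds: "A comparison between intervention arms will be performed". That sentence names no method. The method comes from section 3.1: "Categorical safety data will be analyzed, compared between treatment arms, using the exact contingency table method", that is, Fisher's exact test. The safety population is defined there as "those subjects that are randomized and took at least one dose of study drug".

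The SAP gives no risk difference, risk ratio, odds ratio, confidence interval or margin for any AE comparison. The MMRM in section 5 covers blood pressure and heart rate only.

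Section 2 describes the study as "a pilot trial of between 25-80 participants". The smallest size it works out is "for delta = 1.2 the required sample size is 30 (20 in the prazosin group, and 10 in the control group"), and the largest is 80, split 53 and 27.

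**The concern.** There are two linked problems.

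- **Endpoint.** 1f is about how many participants have AEs. The test beside it is about how many leave because of them. A participant can have AEs, even serious ones, and stay in the trial. The overview in section 5 itself lists AE discontinuation and TEAEs as separate items.
- **Inference.** 1f predicts no difference, but every method named for AE counts is a test of difference. Failing to reject in such a test says little about how large a difference might be, least of all in a small trial with 2:1 allocation.

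At stake is what the trial may say about safety. If 1f is reported through the test beside it, a non-significant dropout result will stand next to a statement on AE incidence that it did not examine. Even with the right endpoint, a p-value alone would not show whether the data exclude a sizeable excess on prazosin.

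**Working it through.** The SAP states no AE rate, margin, safety power or interval, so there is no figure of its own to reproduce. The check uses the splits listed in section 2 (20/10, 27/13, 33/17, 43/22, 53/27, prazosin/placebo). It applies a two-sided 5% level, which section 4.1 states for the primary outcome and which is assumed here for safety.

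**1. How large an imbalance stays non-significant (no AE rates assumed).** Fisher's p-value fixes the total number of events and sums the hypergeometric probabilities of all tables no more likely than the one observed. For 7/20 vs 0/10 the total is 7, and the probability of k placebo events is C(10,k) × C(20,7-k) / C(30,7), with C(30,7) = 2,035,800.

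- k=0: 77,520 / 2,035,800 = 0.0381
- k=5: 252 × 190 / 2,035,800 = 0.0235
- k=6: 210 × 20 / 2,035,800 = 0.0021
- k=7: 120 / 2,035,800 = 0.0001
- Sum: p = 0.064

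So 35% against 0% is non-significant. The smallest prazosin count that reaches p≤0.05 is:

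| Split | 0 placebo events | 1 placebo event |
|---|---|---|
| 20/10 | 8 (40%), p=0.029 | 10 (50%), p=0.0485 |
| 27/13 | 8 (30%), p=0.037 | 12 (44%), p=0.030 |
| 33/17 | 8 (24%), p=0.039 | 11 (33%), p=0.039 |
| 43/22 | 8 (19%), p=0.044 | 11 (26%), p=0.047 |
| 53/27 | 8 (15%), p=0.046 | 13 (25%), p=0.027 |

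At 53/27, 12 against 1 just misses (p=0.0508).

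**2. What a p-value of 1 leaves open (illustrative counts).** Take 10/20 vs 5/10, a difference of 0. The Wilson 95% half-width is 1.96 × √(p(1-p)/n + 1.96²/(4n²)) / (1 + 1.96²/n).

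- Prazosin: 1.96 × √(0.0125 + 0.0024) / 1.192 = 0.201
- Placebo: 1.96 × √(0.0250 + 0.0096) / 1.384 = 0.263
- The Newcombe interval combines them: 0 ± √(0.201² + 0.263²) = ±0.331

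| Counts | Difference, points (95% CI) | Fisher p |
|---|---|---|
| 10/20 vs 5/10 | 0 (-33 to +33) | 1.0 |
| 26/53 vs 13/27 | +1 (-21 to +23) | 1.0 |
| 6/20 vs 1/10 | +20 (-14 to +43) | 0.37 |
| 16/53 vs 3/27 | +19 (-1 to +34) | 0.09 |

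**3. Exact Fisher power (assumed rates).** Rejection probabilities are summed over both binomial distributions, prazosin rate first.

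| Endpoint and rates | 20/10 | 27/13 | 33/17 | 43/22 | 53/27 |
|---|---|---|---|---|---|
| Any AE endpoint, 30% vs 10% | 10% | 18% | 28% | 39% | 47% |
| Any AE endpoint, 40% vs 5% | 43% | 62% | 78% | 90% | 96% |
| Any TEAE, 80% vs 40% | 54% | 67% | 79% | 88% | 94% |
| AE dropout, 10% in both arms | 1% | 2% | 3% | 3% | 3% |

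The last two rows show why the link between hypothesis and endpoint matters. If TEAEs doubled while AE dropout was equal, the test beside 1f would almost never signal it. The TEAE comparison, which the SAP also plans, would find it more often than not at every listed split.

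**The case against.** The strongest reply is that the whole of section 5 is the plan for 1f. The overview covers TEAEs and SAEs, the arms are compared, and section 3.1 supplies both the test and the population. This stands. A reader might infer from the sentence after 1f that AE incidence is never tested, and the SAP does not support that. The gap is one of linkage: the only analysis named with 1f is the dropout test.

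A second reply is that the SAP nowhere says a p-value above 0.05 confirms 1f, and that the hypothesis may only record an expectation. This also stands. The inference that the sponsor plans to claim equal safety from non-significance goes beyond the text. However, the SAP gives no other criterion for judging 1f, and a hypothesis of no difference paired with a difference test invites that reading.

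Third, counts and percentages by arm are planned, so a reader could derive an interval, and the SAP does not spell out intervals for the primary analysis either. That lowers the cost of the omission. It does not make the p-value suitable for the statement in 1f, and naming the endpoint and method in advance removes a choice after the data are seen.

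Finally, low power is common to all small pilots, and the rates in step 3 are assumed. Both are true. A large excess, such as 40% vs 5%, would often be detected. Step 1 needs no assumed rate.

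**Conclusion.** The point holds as a modest correction to the safety inference. 1f is worded for AE incidence and attached to a test of AE dropout. The comparisons that do address incidence are not tied to it, and none of them yields an effect estimate or interval.

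At 20/10, a split of 35% against 0% is non-significant. A p-value of 1.0 there can go with an interval reaching 33 points either way, and still about 21 to 23 points at 53/27. A non-significant Fisher result therefore cannot support 1f at these sizes.

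The thresholds rest only on the splits in section 2 and a two-sided 5% level. The intervals rest on illustrative counts and the power figures on assumed rates. The primary analysis is unaffected. The planned counts, summaries by system organ class and preferred term, listings, and blood pressure and heart rate analyses limit the harm.

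**What to change.** - Restate 1f as estimation of the between-arm difference in AE incidence.
- Tie it to the proportion of participants with any TEAE in the safety population of section 3.1. List any SAE and dropout due to AEs as separate endpoints.
- For each of the three, report the risk difference (prazosin minus placebo) with a 95% confidence interval by one method named in advance, for example the Newcombe hybrid score interval. No margin is needed.
- Keep Fisher p-values as descriptive, and state that a p-value above 0.05 will not be read as no difference.

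The cost is a change of wording and three intervals from counts already planned. The downside is that wide intervals become visible.

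The interval and the Fisher p-value can also disagree near the boundary. For 7/20 vs 0/10 (Fisher p=0.064), the Wilson limits are 0.181 to 0.567 and 0 to 0.278. The Newcombe lower limit is 0.35 - √((0.35 - 0.181)² + 0.278²) = +0.025, just above zero. The SAP should therefore say that the interval carries the interpretation.

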#### 6. Software

Statistical software R (version 4.1.2) will be used http://www.r-project.org.

